10 TREATMENT OF SUBJECTS

10.1 Identity of Investigational Product

The investigational product in this trial is NAL ER tablets or matching placebo tablets. The NAL ER tablets are either round, white to off-white, film-coated tablets containing either 27 or 54 mg of nalbuphine (equivalent to approximately 30 or 60 mg nalbuphine HCl); or oval, white to off-white, film-coated tablets containing 162 mg of nalbuphine (equivalent to approximately 180 mg

nalbuphine HCl). The 27 and 54 mg NAL ER round tablets are identical in appearance. Matching placebo tablets will be used for both tablet shapes (round tablets to represent the 27 and 54 mg tablets, and oval shaped tablets to represent the 162 mg tablets).

All investigational product will be supplied by the Sponsor.

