10.1.2 Down-titration

At the regularly scheduled study visits for Week 28, Week 32, and Week 36, an elective dose reduction to a 108 mg NAL ER BID dose may be considered for subjects who achieve a confirmed WI-NRS \leq 3 **and** visible lesion healing as assessed by an improvement of at least 1 category in the PAS healing activity score, Item 5b. For example, if “0-24%” of PN lesions at baseline were assessed as ‘healed’, then a 1-category change means that “25-50%” of current Week 28 PN lesions are now evaluated as ‘healed’. The WI-NRS scores at and after Week 24 will be available to site staff via the Trialogics portal in order to assess eligibility for this down-titration. The decision to dose reduce is at the discretion of the Investigator and with the agreement of the subject, but once this dosing has started, no re-escalation is permitted. Dose reduction is not permitted prior to Study Week 28 or after Study Week 36.

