8.4.2 Treatment compliance

Compliance in the double-blind period (%) = Number of double-blind period tablets subject actually took/ Number of double-blind period tablets subject was expected to take*100. In the double-blind titration period, a subject is expected to take 3 tablets in the AM and 3 tablets in PM for two weeks, with the exception of Day 1, on which they take only the PM dose. In the double-blind fixed-dose period, a subject is expected to take 1 tablet each in the AM and PM. The number of double-blind period tablets a subject was expected to take is the sum of {6 x [last dose date of double-blind titration – first dose date of double-blind titration +1] – 3} and {2 x [last dose date of double-blind fixed-dose – first dose date of double-blind fixed-dose +1]}. The number of double-blind period tablets a subject actually took will come from the pill counts from the eCRF, i.e., the number of tablets dispensed - the number of tablets returned from the blister cards and bottles for the double-blind period.

Compliance in the open-label period (%) = Number of tablets subject actually took during open-label period/ Number of tablets subject was expected to take during open-label period*100. The compliance is calculated similarly to the double-blind period. The number of tablets a subject was expected to take is the sum of {6 x [last dose date of extension titration – first dose date of extension titration +1] – 3} and {2 x [last dose date of open-label fixed-dose period – first dose date of open-label fixed-dose period +1]}.

Number of tablets a subject actually took during open-label period is calculated by the number of tablets dispensed - the number of tablets returned from the blister cards and bottles for the open-label period. Study drug compliance will be summarized by treatment group, with the number of subjects (n), mean, standard deviation, standard error, median, minimum, and maximum. They will also be summarized in categories “< 50% compliant” and “≥ 50% compliant” using frequency tables. Also, the categories of “< 60% compliant” and “≥60% compliant” will be provided by count and percentage. By-subject listings will also be provided.

Study drug compliance summaries will be based on the Safety Population.

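### The open-label compliance denominator in SAP 8.4.2 stays at 2 tablets a day after reduction to 108 mg BID, so compliance is overstated for every subject who reduces

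*SAP*

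**What the plan says.** SAP 8.4.2 defines one open-label compliance percentage, introduced by "The compliance is calculated similarly to the double-blind period". Its parts are:

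- Numerator: a physical count, "the number of tablets dispensed - the number of tablets returned from the blister cards and bottles for the open-label period".
- Denominator: an extension-titration term, "6 x [last dose date of extension titration – first dose date of extension titration +1] – 3", plus a fixed-dose term, "2 x [last dose date of open-label fixed-dose period – first dose date of open-label fixed-dose period +1". Neither has a provision for a changed dose.
- Reporting: summary statistics including the maximum, by-subject listings and categories: "They will also be summarized in categories “< 50% compliant” and “≥ 50% compliant” using frequency tables". A second cut at 60% is also tabulated.

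Protocol 10.1.2 provides that at Weeks 28, 32 and 36 "an elective dose reduction to a 108 mg NAL ER BID dose may be considered" for subjects who meet itch and lesion-healing criteria. The reduction cannot be reversed. SAP 8.4.3 counts the subjects who reduce, but does not carry the reduction into the compliance formula.

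Protocol 10.1 describes round "film-coated tablets containing either 27 or 54 mg of nalbuphine" and oval tablets of 162 mg. Protocol 10.1.1 has tablets taken whole. Protocol 10.4 defines percent compliance relative to what the subject was prescribed or should have taken in the interval.

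**The concern.** The multiplier of 2 is right while the dose is one 162 mg tablet twice a day. After a reduction it no longer matches what the subject is told to take, because no single listed tablet delivers 108 mg. The numerator counts the extra tablets and the denominator does not, so the percentage is too high.

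This is also a departure from Protocol 10.4 that SAP Section 9, the list of changes from the protocol, does not mention.

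At stake is how the open-label compliance tables read. Correctly dosed reduced subjects would look like over-users of an opioid-class drug, and the 50% and 60% categories would not mean what their labels say for them. Reduction is offered to subjects with low itch and healing lesions, so the error falls on good responders. Its frequency may differ between the groups by which the table is split.

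**Working it through.** The SAP gives a formula and no number, so there is no stated figure to reproduce. I checked first that the formula works without a reduction.

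**Inputs**
- Extension titration: 14 days (Protocol 10.1.1, two-week card).
- Open-label fixed-dose period: Days 113 to 364 (Protocol Tables 1 and 2), so 364 − 113 + 1 = 252 days.
- Reduction visits: Days 196, 224 and 252 (Protocol Table 2).
- Tablet strengths: 27, 54 and 162 mg, whole tablets.

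**Baseline check.** Expected = (6 × 14 − 3) + 2 × 252 = 81 + 504 = 585. A Week 52 completer who stays on 162 mg BID and takes everything has 585/585 = 100%.

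**Tablets per 108 mg dose.** The only whole-tablet combinations are 2 × 54 (two tablets), 54 + 2 × 27 (three) and 4 × 27 (four). Per day that is 4, 6 or 8, never 2.

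**Prescribed tablets after a reduction.** Prescribed = 81 + 2 × (days before) + k × (days after), with k tablets a day. Days before/after, counting the visit day at the old rate: 84/168 (Week 28), 112/140 (Week 32), 140/112 (Week 36). With k = 4:

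- Week 28: 81 + 168 + 672 = 921
- Week 32: 81 + 224 + 560 = 865
- Week 36: 81 + 280 + 448 = 809

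**Results under the SAP formula (denominator 585)**

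| | Week 28 | Week 32 | Week 36 |
|---|---|---|---|
| Fully adherent, k = 4 | 157.4% | 147.9% | 138.3% |
| Fully adherent, k = 6 | 214.9% | 195.7% | 176.6% |
| Fully adherent, k = 8 | 272.3% | 243.6% | 214.9% |
| True 50% throughout, k = 4 | 78.7% | 73.9% | 69.1% |
| True adherence below which the <50% category applies, k = 4 | 31.8% | 33.8% | 36.2% |
| True adherence below which the <60% category applies, k = 4 | 38.1% | 40.6% | 43.4% |

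Examples for Week 28: 921/585 = 157.4%; 0.5 × 921/585 = 78.7%; 0.5 × 585/921 = 31.8%; 0.6 × 585/921 = 38.1%. Starting the new rate on the visit day itself raises the first row only to 157.8%, 148.2% and 138.6%.

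**After correction.** With 921, 865 or 809 in the denominator, the fully adherent subject scores 100% and the half-adherent subject 50%.

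**The case against.** The best defence is that this is one descriptive percentage, in an open-label period, for a subset whose size the documents do not give, and that other checks exist. Sites reconcile returned tablets with e-diary dosing entries (Protocol 10.1.1 and 10.4), and the SAP's maximum and by-subject listings would show values far above 100%. That limits the consequence, and it stands. It does not make the reported percentage right, and a poorly adherent reduced subject at 70% to 80% would not stand out.

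The tablet count is also inferred: the protocol refers to a Pharmacy Manual for dosing details, and Table 2 has no separate supply entry for reduced subjects. That stands as a limit on the size, not the direction, since the listed strengths rule out one tablet per dose.

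A reader might infer more than the documents support:

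- **That the categories cannot flag reduced subjects.** They can, but only at much lower true adherence than the labels state.
- **That a fully adherent subject scores 167% or 144%.** Those are the fixed-dose segment alone (840/504 and 728/504). The SAP percentage includes the 81 titration tablets.
- **That taking everything before Week 28 and half afterwards proves misclassification.** Such a subject shows (81 + 168 + 336)/585 = 100%, but true adherence is 585/921 = 63.5%, which is in the upper category at both cuts anyway. The subject at 50% throughout is the better example: the 60% cut should flag that subject and does not.
- **That long-term safety exposure is misstated.** SAP 7.2.6 and 8.4.1 compute exposure from dose dates, and the exposure-adjusted event rates in SAP 8.7.1 are per subject-year. As described, neither uses tablet compliance.

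**Conclusion.** The formula is wrong as written for every subject who reduces. At the minimum of 4 tablets a day, a fully adherent Week 52 completer is overstated by 38 to 57 percentage points, depending on the reduction visit. The 50% category catches a reduced subject only below about 32% to 36% true adherence, and the 60% category only below about 38% to 43%.

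These figures rest on treatment to Day 364 and on the assumed 4 tablets a day; 6 or 8 a day makes the error larger. Subjects who stop soon after reducing are affected less.

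The effect is confined to the open-label compliance summaries, categories and listings. Reduction is barred before Week 28, so the Week 14 endpoint and double-blind compliance are untouched. This is a minor correction, but it changes reported numbers.

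**What to change.** In SAP 8.4.2, split the fixed-dose term at the recorded reduction visit or date: 2 × days before it, plus the tablets prescribed per day × days after it. That agrees with Protocol 10.4. Alternatively, compute open-label compliance in doses or in mg, which avoids dependence on tablet strength. State in the SAP how many tablets make up a 108 mg dose.

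The programming cost is a formula edit. The one thing to confirm first is that the exposure data hold the reduction date and the dispensed strength. SAP 8.4.3 implies that the reduction visit is known, but neither document names a date field. If only the visit is recorded, its date can serve as the split point. No dose or clinical rule changes.

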8.4.3 Treatment dose reduction

The count and percentage of subjects who reduced their dose per protocol (at weeks 28, 32 or 36) will be summarised by prior treatment group on the Safety Population.

8.5 Efficacy analyses

8.5.1 Analysis methods

8.5.1.1. Logistic Regression Analysis

The primary efficacy endpoint (and other binary efficacy endpoints) “responder type” efficacy endpoints will be analyzed with a logistic regression model with baseline score as a covariate and site (USA versus other) as a fixed effect. The logistic regression model will provide estimated response rates, standard error, odds ratio (OR), two-sided 95% confidence interval for OR, and p-values at Week 14.

8.5.1.2 Mixed model repeated measures analysis

A mixed model repeated measures analysis using ‘direct likelihood’ will be performed for continuous efficacy outcomes. The SAS procedure PROC MIXED will be used. The preferred model will include the fixed effects of treatment, visit, treatment-by-visit interaction, and the baseline value of the endpoint variable as a covariate. An unstructured matrix for the variance-covariance will be used. The denominator degrees of freedom will be calculated according to the Kenward-Roger method.

In case of non-convergence of the preferred model or memory issues, the following back-up models are defined:

1. The same as the preferred model, but the Kenward-Roger method will be replaced by Satterthwaite approximation.

2. The same as the preferred model, but with handling of the selection of the covariance structure for the final model in a hierarchical fashion, with the order being Toeplitz, AR (1), and compound symmetry, respectively.

The second back-up model will only be used if the first back-up model does not converge or has memory issues.

The model will provide least-squares mean estimates, standard errors, two-sided 95% confidence intervals and p-values (where applicable) for mean change at all visits between treatments (NAL ER vs. placebo).

8.6. Multiplicity

In order to control for Type, I error (0.05), a fixed sequence testing procedure will be used on the primary and 3 key secondary endpoints. All endpoints will be tested (NAL ER treatment arm versus the placebo arm) at the 0.05 level of significance, following a pre-specified order. As soon as one endpoint assessment is found to be non-significant, subsequent endpoints will not be assessed. The rank order of testing is specified below.

- Time to onset of effect on pruritus as measured by proportion of participants with an improvement (reduction) in WI-NRS by ≥ 4 from baseline during the 14-week treatment period.
- Change in Investigator Global Assessment-Prurigo Nodularis (IGA-PN) as assessed by the percentage of subjects having a 1-category improvement in activity.
- The mean change in 7-day average WI-NRS from baseline to Week 14 for the NAL ER treatment arm versus the placebo arm.
- Change in PAS as assessed by the percentage of subjects having a 1-category improvement in the percentage of prurigenous lesions with excoriations/crusts (item 5a) from baseline to Week 14 for the NAL ER treatment arm versus the placebo arm.
- Change in PAS as assessed by the percentage of subjects having a 1-category improvement in the percentage of healed lesions (item 5b) from baseline to Week 14 for the NAL ER treatment arm versus the placebo arm.
- Change in PAS as assessed by the percentage of subjects having a 1-category improvement in the percentage number of lesions (item 2) from baseline to Week 14 for the NAL ER treatment arm versus the placebo arm.
- The mean change in ItchyQoL from baseline to Week 14 for the NAL ER treatment arm versus the placebo arm.

- The mean change in sleep disturbance (PROMIS Sleep Disturbance Short Form 8a) from baseline to Week 14 for the NAL ER treatment arm versus the placebo arm.
- The proportion of subjects having a PBI-P score of ≥ 1 at Week 14 for the NAL ER treatment arm versus the placebo arm.

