8.6 Analysis of Primary Efficacy Endpoint

Hypothesis:

The null hypothesis is that there is no treatment group difference (NAL ER vs. placebo) for the primary efficacy endpoint and the alternative hypothesis is that a treatment group difference exists.

Statistical Decision Rules

Unless otherwise indicated, all tests will be 2-sided, and differences resulting in a p-value <0.05 will be considered statistically significant.

The primary efficacy endpoint is the difference between the percent responders at Week 14 for the NAL ER treatment arm versus the placebo arm.

A responder is defined as a subject with a ≥ 4 -point decrease in the 7-day average WI-NRS from baseline to Week 14.

The proportions of responders in NAL ER and placebo will be compared using a logistic regression model, with baseline WI-NRS as a covariate and country as fixed effect, as described below. Missing Week 14 WI-NRS data will be set to missing.

Sample SAS code:

```
proc genmod data=winrsa descending; where avisitn ge 3;
class usubjid avisitn trt posite ;
model resp = trt avisitn avisitn*trt posite base
/ dist=binomial;
repeated subject=usubjid / withinsubject=avisitn
type=un;
lsmeans trt*avisitn /cl ilink diff oddsratio;
Ods output diff=diff lsmeans=lsm ;
run;
```

* Estimate Response rate and SE;

Recoding the resp to a new resp variable

```
data winrsa; set winrsa;
if resp = 0 then respnw = 2;
else if resp= 1 then respnw = 1;
run;
```

Using proc freq to create the binomial dataset;

```
proc sort data = winrsa; by avisitn trt;
proc freq data = winrsa; by avisitn trt;
tables respnw/ out = FreqCount binomial ;
exact binomial;
ods output binomial=bin;
run;
```

The variable *_bin_* is the response rate for resp = 1;
The variable for SE is *E_bin*

* Estimate Odds ratio and CI;

These are provided in the diff dataset and can be output directly.

run;

Sensitivity analysis

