8.6.3 Analysis of secondary efficacy endpoints

All secondary endpoints will be analyzed using the mITT population.

MMRM without imputation for missing data:

The following secondary efficacy endpoints will be analyzed using a mixed model for repeated measures (MMRM):

- The mean change in 7-day average WINRS from baseline to Week 14 for the NAL ER treatment arm versus the placebo arm;
- The mean change in ItchyQoL from baseline to Week 14 for the NAL ER treatment arm versus the placebo arm;
- The mean change in sleep disturbance (PROMIS Sleep Disturbance Short Form 8a) from baseline to Week 14 for the NAL ER treatment arm versus the placebo Arm.

The analysis of change from baseline to week 14 will be performed utilizing all observed data for visits up to and including Week 14, without imputation for missing data. The model used for this analysis will include the fixed effects of treatment, visit, treatment-by-visit interaction, and baseline value. An unstructured variance-covariance matrix will be used in the analyses. The comparison of interest is the treatment difference at Week 14. The model will provide least-squares mean estimates, standard errors, two-sided 95% confidence intervals and p-values for mean change at all time points between treatments (NAL ER vs. placebo) for ItchyQoL (total score and subscales: symptoms, functional limitations, emotions) and PROMIS. The same statistics will be provided for WI-NRS, except for the p-values.

Sample SAS code:

```
PROC MIXED data=xxxx;
  CLASS visit treatment subjid;
  MODEL CHG = treatment visit treatment*visit baseline/solution DDFM=KENWARDROGER;
  REPEATED visit / type=un subject=subjid;
  LSMEANS treatment*visit / pdiff CL;
  ODS output Diffs=outdata1 LSMeans=outdata2;
RUN;
```

Sensitivity analyses: MMRM with imputation for missing data

We will use the imputation methods described above for the primary efficacy endpoints to assess the sensitivity of missing data on inference regarding the secondary endpoints. Since these are continuous measures, we will use the delta methods described above.

Summary for Categorical Endpoints:

The count and percentage will be provided for the following endpoints:

- Change in PAS as assessed by the percentage of subjects having a 1-category improvement in the percentage of prurigenous lesions with excoriations/crusts (item 5a) from baseline to Week 14 for the NAL ER treatment arm versus the placebo arm;

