- Change in PAS as assessed by the percentage of subjects having a 1-category improvement in the percentage of healed lesions (item 5b) from baseline to Week 14 for the NAL ER treatment arm versus the placebo arm;
- Change in PAS as assessed by the percentage of subjects having a 1-category improvement in the percentage number of lesions (item 2) from baseline to Week 14 for the NAL ER treatment arm versus the placebo arm;
- Change in IGA-PN as assessed by the percentage of subjects having a 1-category improvement in activity from baseline to Week 14 for the NAL ER treatment arm versus the placebo arm;
- Change in IGA-PN as assessed by the percentage of subjects having a 1-category improvement in stage from baseline to Week 14 for the NAL ER treatment arm versus the placebo arm;
- The proportion of subjects with PBI-P ≥ 1 at Week 14 for the NAL ER treatment arm versus the placebo arm;
- The proportion of subjects with PBI-P ≥ 2 at Week 14 for the NAL ER treatment arm versus the placebo arm;
- The proportion of subjects with PBI-P ≥ 3 at Week 14 for the NAL ER treatment arm versus the placebo arm.

In addition, shift tables from baseline for improved ≥ 1 , no change, worsened ≥ 1 , and discontinued at Week 14 will be presented for PAS (item 5a), PAS (item 5b), PAS (item 2), IGA-PN for Activity, and IGA-PN for Stage.

Logistic Regression for Categorical Endpoints

The logistic regression model used for the primary endpoint will also be used for several secondary efficacy endpoints. Subjects with missing Week 14 measurement are treated as non-responders. Response rate, standard error, OR between the treatment groups, 95% confidence interval and p-values will be provided. The endpoints are:

- Change in PAS as assessed by the percentage of subjects having a 1-category improvement in the percentage of pruriginous lesions with excoriations/crusts (item 5a) from baseline to Week 14 for the NAL ER treatment arm versus the placebo arm;
- Change in IGA-PN as assessed by the percentage of subjects having a 1-category improvement in activity from baseline to Week 14 for the NAL ER treatment arm versus the placebo arm (95% CI only, with no p-value).

Sensitivity analysis for PAS (item 5a)

The sensitivity analysis to assess the impact of concomitant medications use for the primary endpoint will also be used for PAS (item 5a).

For open-label period visits, descriptive statistics will be displayed by treatment and overall for all secondary variables.

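### The SAP's fixed sequence announces four endpoints, ranks nine without placing the Week 14 responder, and opens with three steps that have no usable p-value

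*SAP*

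**What the plan says.** SAP 8.6 (Multiplicity) states that "a fixed sequence testing procedure will be used on the primary and 3 key secondary endpoints", each at 0.05, and that testing ends at the first non-significant result. The list that follows has nine items:

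1. time to onset
2. IGA-PN activity
3. mean change in WI-NRS
4. PAS item 5a
5. PAS item 5b
6. PAS item 2
7. ItchyQoL
8. PROMIS sleep
9. PBI-P of at least 1

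The first item begins "Time to onset of effect on pruritus as measured by proportion of participants with an improvement (reduction) in WI-NRS" and refers to a drop of at least 4 points over the 14-week period. The Week 14 responder has its own rule in the next section, Analysis of Primary Efficacy Endpoint: "differences resulting in a p-value <0.05 will be considered statistically significant".

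The planned outputs are set elsewhere. SAP 8.5.1.1 covers the primary and other binary endpoints and promises "two-sided 95% confidence interval for OR, and p-values at Week 14". SAP 8.6.3 is narrower:

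- For the mean WI-NRS change: "The same statistics will be provided for WI-NRS, except for the p-values".
- For IGA-PN activity: "95% CI only, with no p-value".
- For the categorical endpoints as a group: "The count and percentage will be provided for the following endpoints".
- For the regression: "The logistic regression model used for the primary endpoint will also be used for several secondary efficacy endpoints". The list under that sentence holds only PAS 5a and IGA-PN activity.

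SAP Section 9 says that ItchyQoL and PROMIS were taken out of the ranking in favour of PAS 5a. The SAP's endpoint section still names ItchyQoL, PAS 5a and PROMIS as the key secondaries, and Appendix 12.3 names the same three as the secondary endpoints. Protocol 13.4.6.3 has a four-step order: Week 14 responder, ItchyQoL, PAS 5a, PROMIS.

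**The concern.** A fixed sequence protects the type I error only if the order is settled in advance and every step returns a clear pass or fail. Here the announced number of endpoints does not match the list, the head of the chain is not stated, and several links have no decision attached.

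What is at stake is the standing of the secondary claims. If the list is followed literally, no secondary endpoint can be reached and none is confirmatory. If someone decides later which section governs, the order is no longer fixed in advance. ItchyQoL shows the spread: it is the first secondary in the protocol, seventh in SAP 8.6, and excluded according to SAP Section 9.

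Changing the protocol's order is not itself the fault. The change is declared in SAP Section 9 and in the version history (Final 2.0, 25 March 2022). That date falls after the December 2021 Week 14 date planned in the protocol synopsis. Nothing in the documents says the blind had been broken, but a late change makes one unambiguous order more important.

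**Working it through.** **The plan's own count.** One primary plus three key secondaries is 1 + 3 = 4. The SAP's endpoint section (ItchyQoL, PAS 5a, PROMIS) and Protocol 13.4.6.3 both reproduce this. The ranked list in SAP 8.6 has 9 entries, and none is the Week 14 responder.

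**Each ranked step against its planned output.**

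| Rank | Step | Planned output | Status |
|---|---|---|---|
| 1 | Time to onset | Not in the endpoint section; no contrast assigned | No clear test |
| 2 | IGA-PN activity | 8.6.3: logistic model, interval only | p-value withheld |
| 3 | Mean WI-NRS change | 8.6.3: MMRM without p-value | p-value withheld |
| 4 | PAS 5a | 8.6.3: logistic model with p-value | Clean |
| 5 | PAS 5b | 8.5.1.1: p-value; 8.6.3: counts only | Conflict |
| 6 | PAS item 2 | Same as rank 5 | Conflict |
| 7 | ItchyQoL | 8.6.3: MMRM with p-value | Clean |
| 8 | PROMIS sleep | 8.6.3: MMRM with p-value | Clean |
| 9 | PBI-P of at least 1 | 8.5.1.1: p-value; 8.6.3: counts only | Conflict |

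Totals: 3 clean + 2 withheld + 3 in conflict + 1 unclear = 9. Steps that need a further decision: 2 + 3 + 1 = 6 of 9.

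**Where the gate stops.** Put the Week 14 responder first by implication and suppose it succeeds. The next step is rank 1, which has no defined pass or fail. Ranks 2 and 3 follow, and 8.6.3 withholds the p-value for both. Rank 4 is the first step that can be decided, and it can be reached only by passing three that cannot. Six steps precede ItchyQoL at rank 7. Of these, ranks 1, 2, 3, 5 and 6 are not cleanly testable, which is 5 of 6.

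**Type I error.** A single chain with one head keeps the familywise error at 0.05 whatever its length, so nine steps instead of four is not in itself inflationary. Inflation would arise only if the Week 14 responder were tested at 0.05 outside the list while the list started its own 0.05 chain. With two independent heads that gives 1 − 0.95² = 0.0975. The SAP does not say it intends this, so no inflation is claimed. It is, however, a reason to write the responder's position down.

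**The case against.** The best defence is that SAP 8.6 governs testing and orders every listed endpoint to be tested at 0.05, so 8.6.3 merely limits what is reported. The sample PROC MIXED code in 8.6.3 requests pairwise differences, which would produce a p-value for rank 3. Rank 2 is binary with a logistic model, and 8.5.1.1 promises p-values for binary endpoints. Rank 1 is phrased as a proportion, so the same model could serve. The primary is named first in the opening sentence of 8.6 and is step 1 in the protocol.

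Some of this stands:

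- Rank 2 is a conflict with 8.5.1.1 as well as a withheld p-value.
- Ranks 7 and 8 are clean only as to model and p-value. If Section 9 is also counted, PAS 5a alone has both an undisputed test and an undisputed place.
- Reading the primary as first is reasonable, and its test is not in doubt.
- The strictest reading is conservative: secondary claims are lost, and none is gained falsely.

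The gate is still not repaired. The statements in 8.6.3 on ranks 2 and 3 are specific and explicit, so a general sentence or a code option does not override them. A confidence interval could serve as the decision, but the SAP states no such rule and defines significance by p-value. Applying the logistic model to rank 1 at Week 14 would simply repeat the primary. The sample GENMOD code offers treatment contrasts at several visits, and none is chosen for this step. Nor does the finding depend on Section 9 or the appendix, because the block at ranks 1 to 3 follows from 8.6 and 8.6.3 alone.

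**Conclusion.** The concern holds. As written, SAP 8.6 gives no confirmatory path to any secondary endpoint: 6 of the 9 ranked steps, including all of the first 3, need a decision the SAP does not contain. The tally judges each step by whether the SAP assigns it an uncontradicted model and p-value, and it lets the specific statements in 8.6.3 prevail where they expressly deny a p-value. The test of the Week 14 responder at 0.05 is unaffected. This must be fixed before unblinding, because afterwards the governing order would be chosen with results in view.

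**What to change.** Before unblinding:

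- State one order in SAP 8.6, with the Week 14 responder explicitly first.
- Plan a model and a p-value in SAP 8.6.3 for every ranked step, and remove the contradiction with 8.5.1.1.
- Define the time-to-onset item (quantity, time point or contrast, and test) or take it out of the chain.
- Bring SAP Section 9, the endpoint section and Appendix 12.3 into line with that order, and label all other endpoints descriptive.

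The choice of order belongs to the sponsor. The protocol's four-step order would need the least work, since all four steps already have planned tests. The cost is SAP wording only, with no new data or visits; some endpoints lose confirmatory status.
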